2.3 Patient disposition, demographics and other baseline characteristics

The number of patients screened and the number of screen failures will be presented (overall).

The number of patients included in each of the Randomized, SAF, FAS, PPS, AUD, PKAS and PKSSAS populations will be summarized for each cohort, treatment arm and overall.

Patients who complete the treatment phase and patients who complete the follow-up phase will be summarized using the FAS. Patients who discontinue from the treatment phase and patients who discontinue the follow-up phase will be summarized overall and by reason for discontinuation using the FAS.

The FAS will be used to summarize the following by cohort and treatment arm:

- Demography: age, age group (< 65 years and >=65 years), gender, race and ethnicity, weight (kg), height (cm), body mass index (BMI).
- Baseline characteristics: baseline spirometry (FEV₁, [REDACTED]) %predicted values, MIC, macrolide use, bronchodilators, inhaled corticosteroids, tobramycin MIC=>8 at baseline, BSI.
- Medical history - ototoxicity
- History of pulmonary exacerbations
- Bronchiectasis-related medical history
- Spirometry assessed at screening
- Previous hospital admissions and exacerbations
- Other relevant medical history

Age will be calculated as the difference between year of birth and year of informed consent.

The following table will be used to derive the BSI:

Table 2-1 Severity criteria for BSI

Criteria/Point	0	1	2	3	4	5	6
Age	<50		50-69		70-79		80+
BMI (kg/m ²)	≥18.5		<18.5				
FEV ₁ % predicted	>80%	50-80%	30-49%	<30%			
Hospital admissions in the past 2 years	No					Yes	
Exacerbation frequency in the last 12 months	0-2		≥3				
MRC dyspnoea	1-3		4	5			
Colonisation status	Not colonised	Chronic colonisation		P.aeruginosa colonisation			
Radiological severity	<3 lobes involved	≥3 lobes or cystic changes					

Medical history recorded in the eCRFs will be reviewed to determine whether a patient had a hospital admission in the past 2 years. The pulmonary exacerbation history eCRF data will be reviewed to determine the exacerbation frequency in the 12 months prior to Screening.

If any individual severity criteria cannot be assessed for a patient due to missing or incomplete data, the BSI total score will not be derived.

Smoking history will be listed in patient listing only.

Listings will be provided to show all demographic and baseline characteristics using the randomized population.

Major protocol deviations will be summarized by cohort and treatment arm using the FAS.

2.4 Treatments (study treatment, rescue medication, concomitant therapies, compliance)

2.4.1 Study treatment / compliance

Overall exposure (days) to study treatment will be summarized in terms of treatment duration, defined as the number of days from the date of first dose of study drug taken to the date of the last dose of study drug taken, inclusive, i.e., date of last dose of study drug – date of first dose of study drug + 1.

Assessment of compliance will be based on the number of unused capsules returned per patient assessed by the Independent Study Coordinators (ISC).

Compliance will be derived using the following formula:

Compliance = (number of actual inhaled capsules / number of intended inhaled capsules during the derived treatment period) * 100%

The number of intended inhaled capsules during the treatment period will be derived as follows:

- Cohort A: 3 * treatment duration
- Cohort B: 5 * treatment duration
- Cohort C: 8 * treatment duration

Compliance will also be assessed by visit period. Four specific periods will be defined, i.e., Visit 101 to Visit 103, Visit 103 to Visit 104, Visit 104 to Visit 105, and Visit 105 to Visit 106. This will be used to review the compliance for each on/off active treatment period for the cyclical TIP/placebo treatment arms.

Descriptive statistics (n, mean, SD, minimum, median, and maximum) will be presented by cohort and treatment arm for the FAS for overall exposure, and both compliance over the treatment period and compliance by visit period. Duration of exposure will be further categorized as ≤ 22 days, 23-28 days, 29-56 days, 57-84 days, 85-112 days, ≥ 113 days, and the number and percentage of patients by cohort and treatment arm will be presented for each category for the FAS.

The number and percentage of patients with study drug compliance $< 80\%$ and $\geq 80\%$ over the treatment period and for each visit period will also be summarized by cohort and treatment arm using the FAS.

Overall duration of study (days), defined as the number of days from the date of randomization to the date of study completion, i.e., date of study completion – date of randomization + 1, will be summarized descriptively (n, mean, SD, minimum, median, and maximum) by cohort and treatment arm for the FAS.

2.4.2 Prior, concomitant and post therapies

The latest version available prior to database lock of the World Health Organization (WHO) drug dictionary will be used to classify prior, concomitant and rescue medications by therapeutic class.

Prior medication is defined as any medication with a stop date prior to the date of the first dose of study drug.

Concomitant medication is defined as any medication with a start date prior to the date of the first dose of investigational product and continuing after the first dose of investigational product or with a start date on or after the date of the first dose of study drug.

Post-treatment medication is defined as any medication with a start date after the date of the last dose of study drug.

Rescue medication for pulmonary exacerbations (including systemic antibiotics) and for bronchospasm is allowed. Use of rescue medication will be recorded on the Concomitant medications/Significant non-drug therapies CRF.

The number and percentage of patients taking prior, concomitant and rescue medications will be summarized by treatment and by Anatomical Therapeutic Classification (ATC) and preferred term. Each prior, concomitant and rescue medication could be classified by more than 1 ATC and will be counted for each. Summary tables will be provided for rescue and concomitant medications started prior to study drug, started on or after the start of study drug and for non-cystic fibrosis bronchiectasis related medications started on or after the start of study drug. Multiple medication usage by a patient in the same category will be counted only once. Summaries will be based on the SAF.

All prior, concomitant and rescue medications and therapies will also be listed.

2.5 Analysis of the primary objective

The analysis of the primary efficacy variable will be based on the FAS.

2.5.1 Primary efficacy endpoint

The primary efficacy variable is the absolute change in the bacterial load in sputum as assessed by the change in log₁₀ CFUs of *P. aeruginosa* from baseline to Day 29 of treatment. The specimens with more than 1 bacterial morphotype, the sum of all bacterial morphotype will be used to calculate change from baseline values.

2.5.2 Statistical hypothesis, model, and method of analysis

The comparisons of 3 doses of active treatment (TIP 3 capsules OD, 5 capsules OD, and 4 capsules BID) versus pooled placebo will be evaluated by testing the following null hypothesis (H₀) versus the alternative hypothesis (H_a):

H₀: TIP treatment arm is equal to pooled placebo group in bacterial load in sputum at Day 29

H_a: TIP treatment arm is not equal to pooled placebo group in bacterial load in sputum at Day 29

The primary efficacy endpoint will be analyzed using the analysis of covariance (ANCOVA) model. The model will contain treatment, baseline CFU (in log₁₀ unit), and baseline macrolide use (yes/no). The adjusted means will be displayed together with the associated standard error and 2-sided 95% CI. Pairwise comparisons of TIP dosing groups will be conducted versus placebo. To control the family-wise type-I error rate (3 dose levels vs. placebo) at the 2-sided 5% significance level, the step-wise Dunnett procedure will be used.

For the primary efficacy analysis, patients from treatment arms TIP and TIP/placebo cyclical regimen will be pooled for each cohort. This is possible because all patients within the same cohort on the TIP treatment arms (cyclical or continuous) are receiving the same treatment during the first 28 days. Placebo patients will be pooled across the 3 cohorts, as the number of placebo capsules is not expected to influence the change in *P. aeruginosa* bacterial counts.

The estimated adjusted treatment difference (TIP – placebo) will be displayed along with the associated standard error, 2-sided 95% CI, and p-value (2-sided).

The estimated treatment difference and CI will be displayed in forest plot for the treatment arms TIP and TIP/placebo cyclical regimen pooled for each cohort vs pooled placebo across 3 cohorts.

For other efficacy analyses up to and including Day 29, patients from treatment arms TIP and TIP/placebo cyclical regimen will be pooled for each cohort; placebo patients will be pooled across the 3 cohorts.

If no *P. aeruginosa* isolated (NPAI) are detected, i.e, no growth detected, at a given visit where the laboratory sample was available at that visit, the value will be imputed as 99 based on the lower limit of detection (dilution factor is currently 1/100). Log 10(99) will be used in the analysis.

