6.4 Efficacy

The following efficacy assessments will be performed:

- *P. aeruginosa*: CFU (sputum) or semi-quantitative culture data (deep-throat cough swabs for non-sputum producing patients)

[REDACTED]

[REDACTED]

[REDACTED]

[REDACTED]

- Anti-pseudomonal antibiotic use (other than study drug)
- Pulmonary exacerbations (total count, rate, severity and time of onset) and related signs and symptoms
- Pulmonary function by using spirometry
- Patient reported outcomes (QOL-B, [REDACTED])

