2.6.1 Secondary endpoints

2.6.1.1 *P. aeruginosa* colony forming units (CFU)

Anti-microbial efficacy of TIP versus placebo over the entire study duration, as measured by the absolute change in log₁₀ CFUs of *P. aeruginosa* in sputum from baseline to each post-baseline visit (Visits 102 (Day 8), 103 (Day 29), 104 (Day 57), 105 (Day 85) and 106 (Day 113)), will be assessed by morphotype and sum of all morphotypes (mucoid, dry, small colony-variants). For patients with a negative *P. aeruginosa* result, i.e, NPAI, the quantitative test result for the analysis will be imputed for each morphotype with log (99) as this represents the detection level for a dilution of 100. Means together with the 95% CIs will be graphically displayed over time. The summaries will be provided by treatment groups Cohort A: TIP, Cohort A: TIP/placebo cyclical, Cohort B: TIP, Cohort B: TIP/placebo cyclical, Cohort C: TIP, Cohort C: TIP/placebo cyclical, Pooled TIP and Pooled TIP/placebo cyclical and pooled placebo. Comparisons between treatment regimens across all cohorts versus pooled placebo will also be analyzed.

The number and percentage for patients with no *P. aeruginosa* in sputum and number and percentage of patients with a positive result of *P. aeruginosa* in sputum will be tabulated by cohort, treatment arm, pooled arms by continuous and cyclic regimens and visit. Percentages will be based on the number of patients for whom microbiology results exist per visit.

The number and percentage of patients with NPAI at 2 consecutive post-baseline visits will also be presented by cohort and treatment arm, pooled arms by continuous and cyclic regimens.

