2.6.3 Statistical hypothesis, model, and method of analysis

In general, unless otherwise specified, the following 6 pairwise comparisons will be performed for the secondary endpoints at the 5% significance level without multiplicity adjustment, wherever an inferential analysis is specified:

- TIP 3 capsules OD versus pooled placebo
- TIP/placebo cyclical 3 capsules OD versus pooled placebo
- TIP 5 capsules OD versus pooled placebo
- TIP/placebo cyclical 5 capsules OD versus pooled placebo
- TIP 4 capsules BID versus pooled placebo
- TIP/placebo cyclical 4 capsules BID versus pooled placebo

Descriptive summary statistics by cohort, treatment arm, pooled treatment arm by regimen and pooled placebo will be provided where applicable.

In addition, data will also be summarized for selected endpoints, by pooling continuous TIP regimens together (i.e. TIP 3 capsules OD. from Cohort A + TIP 5 capsules OD from Cohort B+ TIP 4 capsules BID from cohort C) and pooling cyclic TIP regimens together (i.e. TIP/placebo cyclical 3 capsules OD from Cohort A + TIP/placebo cyclical 5 capsules OD. from Cohort B+ TIP/placebo 4 capsules BID cyclical from cohort C) vs pooled placebo.

In addition, the following 2 pairwise comparisons will be performed for the selected endpoints at the 5% significance level without multiplicity adjustment:

- Pooled TIP continuous regimens versus pooled placebo
- Pooled TIP/placebo cyclical regimens versus pooled placebo.

Forest plot will be plotted for below endpoints in addition to the primary endpoint for each treatment arm across 3 cohorts compared with pooled placebo separately and also for the comparison between pooled TIP continuous (pooled from 3 cohorts) with pooled placebo and for

the comparison between pooled TIP/placebo cyclic (pooled from 3 cohorts) with pooled placebo.

- LS Mean difference in log₁₀ CFUs of *P. aeruginosa* in sputum and CI
- For exposure adjusted rate and CI of pulmonary exacerbations during the study
- For incident rate ratio and CI for anti-pseudomonal antibiotics during the study
- Incident rate ratio and CI hospitalization due to serious respiratory-related AEs across the entire study period
- LS Mean difference in QoL-B RSS and CI

2.6.3.1 *P. aeruginosa* colony forming units (CFU)

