The primary efficacy parameter (CFU) will be analyzed using a similar ANCOVA model as used in primary efficacy analysis at Day 85, Day 113 and Day 169. The model will contain treatment, baseline CFU (in log₁₀ unit), and baseline macrolide use (yes/no).

The analysis will not be performed by the subgroup of morphotypes. Six pairwise comparisons will be evaluated as specified in [Section 2.6.3](#). The estimated adjusted treatment difference for each of the 6 comparisons (TIP–placebo) will be displayed along with the associated standard error, 2-sided 95% CI. In addition, CFU data will be summarized by morphotype and sum of all morphotypes at each scheduled visit.

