2.10 Patient reported outcomes

Quality of Life Questionnaire-Bronchiectasis (QoL- B)

QoL-B is assessed at Visit 2 (Baseline), Visit 102 (Day 8), Visit 103 (Day 29), Visit 104 (Day 57), Visit 105 (Day 85), Visit 106 or TD (Day 113), Follow-up Visit 201 (Day 141) and Follow-up Visit 202 or PSD (Day 169).

The QoL-B consists of 37 items across 8 domains: Physical, Role Functioning, Vitality, Emotional Function, Social Functioning, Treatment Burden, Health Perception and Respiratory Symptoms. Each of the 37 items is scored from 1 to 4.

Items in the questionnaire are expressed either 'negatively' or 'positively', therefore a number of items must be recorded before the scores for each of the domains are calculated. The score is calculated by adding the score obtained for each item of a domain (scale), after any necessary recoding. Scoring for each domain can be computed only if at least half the items have been completed. If not, then the domain should not be scored and should be considered missing for that particular person who filled out the questionnaire.

[figure not shown]
[figure not shown]
Descriptive statistics will be provided for each domain score for all applicable visits for the FAS by treatment arm [and](#) pooled arms by continuous and cyclic regimens. Changes from baseline to each post-baseline visit will also be summarized. For the QoL-B Respiratory Symptom Score (RSS), further summaries will be provided for:

- Patients with/without pulmonary exacerbations during the treatment period
- Patients with overall study drug compliance $\geq 80\%$

The change from baseline in QoL-B RSS will be analyzed using a linear repeated measure model. The model will contain treatment, baseline macrolide use, visit (visits 102 to 202), and treatment-by-visit interaction as fixed effects with baseline QoL-B RSS, baseline-by-visit interaction as covariates. The within-patient correlation will be modeled using the unstructured covariance matrix in the mixed model. If the model does not converge, then the compound symmetry covariance structure will be used. The restricted maximum likelihood method will be used.

QoL-B correlation with other patient reported outcome measures will be performed by RTI health solutions; consequently these are not detailed within this SAP.

Details on deriving the domain scores can be found in [Section 5.5](#).

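### The SAP pools the two TIP regimens by dose through Day 29, but its specified QOL-B outputs and CFU summaries at Days 8 and 29 include no pooled-by-dose result

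*SAP*

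**What the plan says.** **The rule.** SAP 2.5.2 pools the continuous and cyclical arms by dose for the primary Day 29 CFU analysis, then extends this: "For other efficacy analyses up to and including Day 29, patients from treatment arms TIP and TIP/placebo cyclical regimen will be pooled" for each cohort, with placebo pooled over the three cohorts. QOL-B falls under the rule. Protocol 6.4 has an efficacy entry that begins "Patient reported outcomes (QOL-B", and protocol 9.5.1.6 places its analysis among the efficacy variables.

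**The default contrasts.** SAP 2.6.3 says: "In general, unless otherwise specified, the following 6 pairwise comparisons will be performed for the secondary endpoints at the 5% significance level". The six are each continuous and each cyclical arm against pooled placebo. The same section plans a forest plot of "LS Mean difference in QoL-B RSS and CI", by arm and by regimen pooled across doses.

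**The QOL-B model.** SAP 2.10: "The model will contain treatment, baseline macrolide use, visit (visits 102 to 202), and treatment-by-visit interaction as fixed effects". It does not list the levels of treatment or say which contrasts are reported at which visit. The descriptive QOL-B summaries are by treatment arm and regimen pool at all applicable visits.

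**CFU.** SAP 2.6.1.1 includes Days 8 and 29 in its visit list and says: "The summaries will be provided by treatment groups Cohort A: TIP, Cohort A: TIP/placebo cyclical", continuing through the other arms, the two regimen pools and pooled placebo. No group pools the regimens within a dose. The inferential CFU analysis in SAP 2.6.3.1 is run "using a similar ANCOVA model as used in primary efficacy analysis at Day 85, Day 113 and Day 169".

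**The concern.** Up to the Day 29 assessment, the two active arms of a cohort have had the same drug at the same dose. The protocol has PRO questionnaires completed before other assessments at a visit (section 6) and gives QOL-B a one-week recall (6.4.6). Day 29 dosing comes from the newly dispensed kit (5.5.4). The Day 29 QOL-B score therefore reflects the shared first 28 days.

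Separate continuous and cyclical estimates at Days 8 and 29 are two noisier estimates of one dose effect. A reader may also see a gap between regimens that can only be chance. After Day 29 the regimens differ and must be separated, so the model needs seven groups (six active arms and pooled placebo). The early pooled result then has to come from a contrast, and none is written down. The sentence requiring it sits in the primary-endpoint section and is not repeated in 2.6.3 or 2.10, so a programmer could easily miss it.

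**Working it through.** **Inputs.** 180 planned; cohorts 1:1:1; 2:2:1 within cohort; 24 per active arm and 36 placebo in total (protocol 3.1, 3.2). 107 randomised (SAP 1). CFU difference 2.0, SD 2.0, alpha 0.05/3 two-sided, 90% power, 20% discontinuation (protocol 9.7). Secondary comparisons at two-sided 5%, unadjusted (SAP 2.1.2). QOL-B RSS minimal important difference 8 points (protocol 6.4.6). No QOL-B SD is given.

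**Step 1: the plan's own figures.** n per group = 2 × (2.394 + 1.282)² × (2.0/2.0)² = 27.02, so 28; 28/0.8 = 35. The noncentral t gives 29; 29/0.8 = 36.25, so 37. The stated 36 lies between. For power, 48 per dose and 36 placebo become 38.4 and 28.8 after 20% loss, giving 94.2% by noncentral t against the stated 94%. The primary power figure thus already relies on pooling by dose.

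**Step 2: precision by arm and by pooled dose.** SE in SD units = √(1/n_active + 1/n_placebo).

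- Planned, by arm: √(1/24 + 1/36) = 0.2635. Pooled: √(1/48 + 1/36) = 0.2205.
- At 107, expected sizes are 107/3 × 2/5 = 14.27 per active arm, 28.53 per dose and 107/5 = 21.4 placebo. By arm: √(1/14.27 + 1/21.4) = 0.342. Pooled: √(1/28.53 + 1/21.4) = 0.286.
- At both sizes the SE ratio is 1.195 and the variance ratio 1.195² = 1.43.

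**Step 3: can the seven-group model deliver the pooled result?** The variance of 0.5 × (continuous + cyclical) minus placebo, in SD² units, is 0.25 × (1/14.27 + 1/14.27) + 1/21.4 = 1/28.53 + 1/21.4. The SE is again 0.286, so pooled precision is recovered without a second model.

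**Step 4: illustration on the QOL-B scale.** The SD is assumed over 12 to 24. Power is for an 8-point difference (noncentral t, two-sided 5%); half-width is 1.96 × SD × SE. No dropout is allowed for.

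| Assumed SD | Power, planned N: by arm / pooled | Power, 107: by arm / pooled | 95% half-width, 107: by arm / pooled |
|---|---|---|---|
| 12 | 70% / 85% | 47% / 63% | 8.0 / 6.7 |
| 16 | 46% / 61% | 30% / 40% | 10.7 / 9.0 |
| 20 | 32% / 43% | 21% / 28% | 13.4 / 11.2 |
| 24 | 24% / 32% | 16% / 21% | 16.1 / 13.5 |

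**The case against.** Four points can be made for the plan.

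*The default gives way.* The six contrasts apply only where nothing else is specified, and 2.5.2 is such a specification. SAP 2.10 does not invoke the six contrasts or name treatment levels. This stands: a reader might infer that the SAP contradicts itself outright, but the text supports only an unresolved gap. The gap still matters, because every QOL-B display that is specified is by arm or regimen pool.

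*The main early result is safe.* A reader might infer that the early dose effect in general is estimated on half the treated patients, or that the six contrasts split CFU at Days 8 and 29. Neither is supported. Day 29 CFU is pooled by dose in both model and forest plot, and the six CFU contrasts are confined to Days 85, 113 and 169. The exacerbation, antibiotic and hospitalisation contrasts cover periods, not early visits.

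*The CFU and QOL-B summaries are descriptive.* Splitting a table discards no patients, and SAP section 2 allows summaries by cohort/dose and combined treatments. This stands as to harm, but the listed groups still omit the one that 2.5.2 calls for.

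*The stakes are low.* The QOL-B comparison is secondary and unadjusted, and SAP 1 treats all inference as exploratory after early closure. No continuous-versus-cyclical test is planned, so a chance gap would be visual only. Protocol 3.3 ties hoped-for PRO trends to 16 weeks of treatment. All of this stands and limits the weight of the point.

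**Conclusion.** The SAP's specified outputs do not deliver its own pooling rule for QOL-B at Days 8 and 29, or in the CFU summaries at those visits. The inferential cost is confined to QOL-B RSS at two visits: a by-arm contrast has an SE about 19.5% larger than the pooled-by-dose contrast.

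Each by-arm contrast does use half the active patients at a dose (24 of 48 planned), but calling that a halving of information would overstate it, because placebo stays pooled.

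The ratio assumes equal variances, complete data and the planned allocation; the documents do not give arm sizes among the 107. It does not depend on the SD. The power figures do, and are illustrative only. Even pooled, power at 107 is 40% or less for an SD of 16 or more. This is a modest improvement worth making because it costs almost nothing.

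**What to change.** Keep the seven-group repeated-measures model and make three text changes.

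1. SAP 2.10: for Visits 102 and 103, report three dose contrasts, each 0.5 × (continuous + cyclical) minus pooled placebo. Use the six arm contrasts from Visit 104 on. Show the early visits in the QOL-B forest plot, if at all, by pooled dose.
2. SAP 2.6.1.1 and the descriptive part of 2.10: add pooled-by-dose columns for CFU and QOL-B at Days 8 and 29.
3. SAP 2.6.3: state that the pooling rule in 2.5.2 governs through Day 29 and that the six-arm default applies after it.

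The cost is SAP wording, a few contrast statements and some table columns, with no new data. It should be settled before unblinding.
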